### **3.6 Post-Study Drug Study Follow up**

In this study, overall survival is a key endpoint of the study. Post-study follow-up is of critical importance and is essential to preserving subject safety and the integrity of the study. Subjects who discontinue study drug must continue to be followed for collection of outcome and/or survival follow-up data as required and in line with Section 5 until death or the conclusion of the study.

BMS may request that survival data be collected on all treated/randomized subjects outside of the protocol defined window ([Table 5.1-4](#)). At the time of this request, each subject will be

contacted to determine their survival status unless the subject has withdrawn consent for all contacts or is lost to follow-up.

### **3.6.1      *Withdrawal of Consent***

Subjects who request to discontinue study drug will remain in the study and must continue to be followed for protocol specified follow-up procedures. The only exception to this is when a subject specifically withdraws consent for any further contact with him/her or persons previously authorized by subject to provide this information. Subjects should notify the investigator of the decision to withdraw consent from future follow-up **in writing**, if possible. The withdrawal of consent should be explained in detail in the medical records by the investigator, as to whether the withdrawal is from further treatment with study drug only or also from study procedures and/or post treatment study follow-up, and entered on the appropriate CRF page. In the event that vital status (whether the subject is alive or dead) is being measured, publicly available information should be used to determine vital status only as appropriately directed in accordance with local law.

### **3.6.2      *Lost to Follow-Up***

All reasonable efforts must be made to locate subjects to determine and report their ongoing status. This includes follow-up with persons authorized by the subject as noted above. Lost to follow-up is defined by the inability to reach the subject after a minimum of three documented phone calls, faxes, or emails as well as lack of response by subject to one registered mail letter. All attempts should be documented in the subject's medical records. If it is determined that the subject has died, the site will use permissible local methods to obtain the date and cause of death.

If investigator's use of third-party representative to assist in the follow-up portion of the study has been included in the subject's informed consent, then the investigator may use a Sponsor-retained third-party representative to assist site staff with obtaining subject's contact information or other public vital status data necessary to complete the follow-up portion of the study. The site staff and representative will consult publicly available sources, such as public health registries and databases, in order to obtain updated contact information. If after all attempts, the subject remains lost to follow-up, then the last known alive date as determined by the investigator should be reported and documented in the subject's medical records.

## **4            STUDY DRUG**

Subjects should receive nivolumab at a dose of 240 mg as a 30 minute infusion on Day 1 of each 2-week treatment cycle for 8 doses until progression, unacceptable toxicity, withdrawal of consent, the study ends, or until q4w dosing begins, whichever occurs first. Beginning with Dose 9, subjects should receive nivolumab 480 mg as a 30 minute infusion every 4 weeks ( $\pm$  3 days) until progression, unacceptable toxicity, withdrawal of consent, or the study ends, whichever occurs first. Subjects will receive study drug **for the maximum treatment duration of 24 months**.

Study drug includes both Investigational [Medicinal] Product (IP/IMP) consist of the following:

**Table 4-1: Study Drug for CA209627**

Product Description / Class and Dosage Form	Potency	IP/Non-IMP	Blinded or Open Label	Packaging / Appearance	Storage Conditions (per label)
Nivolumab BMS-936558-01 Solution for Injection	40 mg/4 mL and 100 mg (10 mg/mL)	IP	Open Label	Clear to opalescent colorless to pale yellow liquid. May contain particles	2 to 8°C. Protect from light and freezing

There will be no dose escalations or reductions of nivolumab allowed. Subjects may be dosed no less than 12 days from the previous dose during q2w cycles. For q4w dosing cycles, subjects may be dosed within a  $\pm$  3 day window. Premedications are not recommended for the first dose of nivolumab.

Subjects should be carefully monitored for infusion reactions during nivolumab administration. If an acute infusion reaction is noted, subjects should be managed according to [Section 4.5.6](#).

Doses of nivolumab may be interrupted, delayed, or discontinued depending on how well the subject tolerates the treatment. Dosing visits are not skipped, only delayed.

#### **Nivolumab Injection: 40 mg/4 mL and 100 mg/10 mL (10 mg/mL)**

Nivolumab injection is to be administered as an IV infusion through a 0.2-micron to 1.2-micron pore size, low-protein binding in-line filter at the protocol-specified doses. It is not to be administered as an IV push or bolus injection. Nivolumab injection can be infused undiluted (10 mg/mL) or diluted with 0.9% Sodium Chloride Injection, USP or 5% Dextrose Injection, USP to protein concentrations as low as 0.35 mg/mL.

When the dose is fixed (eg, 240 mg flat dose), nivolumab injection can be infused undiluted or diluted so as not to exceed a total infusion volume of 120 mL. Nivolumab infusion must be promptly followed by a flush of diluent to clear the line. Instructions for dilution and infusion of nivolumab injection may be provided in the clinical protocol, pharmacy binder, or pharmacy reference sheet. Care must be taken to assure sterility of the prepared solution as the product does not contain any antimicrobial preservative or bacteriostatic agent.

No incompatibilities have been observed between nivolumab injection and polyvinyl chloride (PVC), non-PVC/non-DEHP (di[2-ethylhexyl]phthalate) IV components, or glass bottles have been observed.

#### **4.1 Investigational Product**

An investigational product, also known as investigational medicinal product in some regions, is defined a pharmaceutical form of an active substance or placebo being tested or used as a

reference in a clinical study, including products already with a marketing authorization but used or assembled (formulated or packaged) differently than the authorized form, or used for an unauthorized indication, or when used to gain further information about the authorized form.

The investigational product should be stored in a secure area according to local regulations. It is the responsibility of the investigator to ensure that investigational product is only dispensed to study subjects. The investigational product must be dispensed only from official study sites by authorized personnel according to local regulations.

#### **4.2 Non-investigational Product**

Not applicable for this study.

#### **4.3 Storage of Study Drug**

The product storage manager should ensure that the study drug is stored in accordance with the environmental conditions (temperature, light, and humidity) as determined by BMS. If concerns regarding the quality or appearance of the study drug arise, the study drug should not be dispensed and contact BMS immediately.

Study drug not supplied by BMS will be stored in accordance with the package insert.

Please refer to [Section 9.2.2](#) for guidance on IP records and documentation.

#### **4.4 Method of Assigning Subject Identification**

The subject number will be assigned through an interactive voice response system (IVRS) once the subject has signed the informed consent form and is registered. Every subject that signs the informed consent form must be assigned a subject number in IVRS. Specific instructions for using IVRS will be provided to the investigational site in a separate document.

The investigator or designee will register the subject for enrollment by following the enrollment procedures established by BMS. The following information is required for enrollment:

- Date that informed consent was obtained
- Date of birth (year of birth only in Germany)
- Gender at birth
- Tumor type

Once enrolled in IVRS, subjects that have met all eligibility criteria will be ready for treatment and drug vial assignment through the IVRS. The following information is required for drug vial assignment and treatment:

- Subject number
- Date of birth (year of birth only in Germany)
- Tumor Type
- Confirmation of receipt of tumor tissue in archival ( $\leq$  3 months old or new biopsy tissue) and blood samples by a central laboratory

#### **4.5 Selection and Timing of Dose for Each Subject**

Subjects will receive treatment with nivolumab 240 mg as a 30 minute IV infusion on Day 1 of a treatment cycle every 2 weeks (14 days) for 8 doses until progression, unacceptable toxicity, withdrawal of consent, the study ends, or until Q4W dosing begins, whichever occurs first. Participants should begin study treatment within 3 calendar days of treatment assignment. Beginning with dose 9 (2 weeks following the 8th dose), subjects will receive treatment with nivolumab 480 mg as a 30 minute IV infusion every 4 weeks (28 days) ( $\pm$  3 days) until progression, unacceptable toxicity, withdrawal of consent, maximum of 24 months of treatment, or the study ends, whichever occurs first.

If required for clinic scheduling, subjects may be treated up to 3 days before or after the scheduled date, ie, at intervals of not less than 12 days from the previous dose during Q2W cycles. For Q4W dosing cycles, participants may be dosed within a  $\pm$ 3 day window. A dose given more than 3 days after the intended dose date will be considered a delay. Subsequent treatments should be based on the actual date of administration of the previous dose of drug.

No dose escalations or reductions of nivolumab are allowed. Dosing visits are not skipped, only delayed.

There are no premedications recommended for nivolumab until infusion reactions have been observed in the subject. Subjects should be carefully monitored for infusion reactions during nivolumab administration. If an acute infusion reaction is noted, subjects should be managed according to [Section 4.5.6](#).

Dose delay criteria, criteria to resume treatment, and treatment discontinuation criteria can be found in Section 4.5.1, [Section 4.5.2](#), and [Section 4.5.3](#), respectively.

Nivolumab infusions are compatible with polyvinyl chloride (PVC) or polyolefin containers and infusion sets, and glass bottles.

##### **4.5.1 Dose Delay Criteria**

Nivolumab administration should be delayed for the following:

- Grade 2 non-skin, drug-related adverse event with the exception of fatigue
- Grade 2 drug-related creatinine, AST, ALT, or total bilirubin abnormalities
- Any Grade 3 skin, drug-related AE
- Any Grade 3 drug-related laboratory abnormality with the following exceptions:
  - Grade 3 lymphopenia or asymptomatic amylase or lipase does not require dose delay
  - Any Grade  $\geq$  3 AST, ALT, Total Bilirubin will require dose discontinuation (See Section 4.5.3 for Treatment Discontinuation Criteria).
- Any adverse event, laboratory abnormality, or intercurrent illness which, in the judgment of the investigator, warrants delaying the dose of study medication.

Subjects who require delay of nivolumab should be re-evaluated weekly or more frequently if clinically indicated and resume nivolumab dosing when re-treatment criteria are met.

#### **4.5.2 Criteria to Resume Treatment**

Subjects may resume treatment with nivolumab when the drug-related AE(s) resolve(s) to Grade  $\leq 1$  or baseline, with the following exceptions:

- Subjects may resume treatment in the presence of Grade 2 fatigue
- Subjects who have not experienced a Grade 3 drug-related skin AE may resume treatment in the presence of Grade 2 skin toxicity
- For subjects with Grade 2 AST, ALT, and/or total bilirubin abnormalities, dosing may resume when laboratory values return to baseline and management with corticosteroids, if needed, is complete.
- Drug-related pulmonary toxicity, diarrhea, or colitis must have resolved to baseline before treatment is resumed. Subjects with persistent Grade 1 pneumonitis after completion of a steroid taper over at least 1 month may be eligible for retreatment if discussed with and approved by the Medical Monitor or designee.
- Subjects with drug-related endocrinopathies adequately controlled with only physiologic hormone replacement may resume treatment after consultation with the BMS Medical Monitor or designee. Adrenal insufficiency requires discontinuation regardless of control with hormone replacement.

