c) Subjects must have received standard-of-care primary treatment for malignancy and standard-of-care for relapse or refractory disease, if treatment exists. For de novo metastatic disease, subjects with recurrent or refractory disease after standard-of-care (first-line or second-line [if treatment exists]) will be eligible for this trial. If there is no standard-of-care treatment for de novo metastatic disease (eg, metastatic carcinoid), subjects are eligible to enroll without prior first-line (or second-line) therapy.

d) For subjects with brain metastases, there must be  $\geq 1$  evaluable lesion outside the brain. Subjects must not be receiving corticosteroids for brain metastasis.

e) Screening laboratory values must meet the following criteria (using CTCAE v4):

- i) WBC  $\geq 2000/\mu\text{L}$
- ii) Neutrophils  $\geq 1500/\mu\text{L}$

- iii) Platelets  $\geq 100 \times 10^3/\mu\text{L}$
- iv) Hemoglobin  $\geq 9.0 \text{ g/dL}$
- v) Serum creatinine  $\leq 1.5 \times \text{ULN}$  or calculated creatinine clearance  $> 40 \text{ mL/min}$  (using the Cockcroft-Gault formula)

*Female CrCl = (140 - age in years) x weight (kg) x 0.85 / (72 x serum creatinine in mg/dL)*

*Male CrCl = (140 - age in years) x weight in kg x 1.00 / (72 x serum creatinine in mg/dL)*

- vi) AST  $\leq 3.0 \times \text{ULN}$
- vii) ALT  $\leq 3.0 \times \text{ULN}$
- viii) Total bilirubin  $\leq 1.5 \times \text{ULN}$  (except subjects with Gilbert Syndrome who must have a total bilirubin level of  $< 3.0 \times \text{ULN}$ ).
- f) Subjects must have measurable disease by CT or MRI per RECIST 1.1 criteria (see [Appendix 4](#))
- g) Eastern Cooperative Oncology Group (ECOG) Performance Status  $\leq 1$  (see [Appendix 2](#))
- h) Life expectancy  $\geq 16$  weeks

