#### **4.5.3 Treatment Discontinuation Criteria**

Nivolumab treatment should be permanently discontinued for the following:

- Any Grade 2 drug-related uveitis, eye pain, or blurred vision that does not respond to topical therapy and does not improve to Grade 1 severity within the re-treatment period OR requires systemic treatment
- Any Grade 3 non-skin, drug-related AE lasting  $> 7$  days, with the following exceptions for laboratory abnormalities, drug-related uveitis, pneumonitis, bronchospasm, neurologic toxicity, hypersensitivity reactions, infusion reactions, and endocrinopathies:
  - Grade 3 drug-related uveitis, pneumonitis, bronchospasm, neurologic toxicity, myocarditis, hypersensitivity reaction, or infusion reaction of any duration requires discontinuation
  - Grade 3 drug-related endocrinopathies adequately controlled with only physiologic hormone replacement do not require discontinuation. Adrenal insufficiency requires discontinuation regardless of control with hormone replacement.
  - Grade 3 drug-related laboratory abnormalities do not require treatment discontinuation except:
    - Grade 3 drug-related thrombocytopenia  $> 7$  days or associated with bleeding requires discontinuation
    - Grade  $\geq 3$  drug-related AST, ALT or total bilirubin requires discontinuation\*
    - Concurrent AST or ALT  $> 3 \times$  ULN and total bilirubin  $> 2 \times$  ULN
- \* In most cases of Grade 3 AST or ALT elevation, study drug(s) will be permanently discontinued. If the investigator determines a possible favorable benefit/risk ratio that

warrants continuation of study drug(s), a discussion between the investigator and the BMS Medical Monitor/designee must occur.

- Any Grade 4 drug-related adverse event or laboratory abnormality (including but not limited to creatinine, AST, ALT, or total bilirubin), except for the following events which do not require discontinuation:
  - Grade 4 neutropenia  $\leq$  7 days
  - Grade 4 lymphopenia or leukopenia or asymptomatic amylase or lipase
  - Isolated Grade 4 electrolyte imbalances/abnormalities that are not associated with clinical sequelae and are corrected with supplementation/appropriate management within 72 hours of their onset

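### Drug-related AST/ALT above 3 × ULN with bilirubin above 2 × ULN, both below Grade 3, reads as delay and possible resumption in Protocol 4.5.1 and 4.5.2 but as permanent discontinuation in 4.5.3

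*Protocol*

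**What the plan says.** Five places in the protocol bear on this.

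- **Section 4.5.1 (delay).** Dosing is delayed for "Grade 2 drug-related creatinine, AST, ALT, or total bilirubin abnormalities". Only Grade 3 or higher AST, ALT or bilirubin is referred on to Section 4.5.3. Delayed subjects restart when the re-treatment criteria are met.
- **Section 4.5.2 (resume).** "For subjects with Grade 2 AST, ALT, and/or total bilirubin abnormalities, dosing may resume when laboratory values return to baseline", provided any corticosteroid management is finished. The and/or wording covers AST/ALT and bilirubin raised together. No exception is made for that combination.
- **Section 4.5.3 (discontinue).** The list opens with "Nivolumab treatment should be permanently discontinued for the following". Within it, a bullet begins "Grade 3 drug-related laboratory abnormalities do not require treatment discontinuation except", and under that come "Grade $\geq 3$ drug-related AST, ALT or total bilirubin requires discontinuation" (with a footnote allowing a benefit/risk discussion for Grade 3 AST or ALT) and then "Concurrent AST or ALT $> 3 \times$ ULN and total bilirubin $> 2 \times$ ULN". The last item states no grade and carries no footnote.
- **Section 3.5.** Subjects must stop study drug for any event in the Section 4.5.3 list.
- **Section 6.6.** The same two laboratory thresholds appear in the definition of potential drug-induced liver injury, with further conditions on cholestasis and on other apparent causes.

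**The concern.** A subject with a drug-related pair just above both thresholds, neither value at Grade 3, is described by two sets of rules with different endings. An investigator who starts at 4.5.1 finds a Grade 2 abnormality, delays, goes to 4.5.2 and may restart at baseline values. Nothing on that path points to the concurrent clause. An investigator who starts at 4.5.3 finds the pair listed for permanent discontinuation.

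The combination is one the sponsor expects to see: SAP Section 7.6.9.5 tabulates exactly this pair. At stake are consistent handling of a hepatic safety signal across sites and, downstream, the counts of adverse events leading to discontinuation (SAP 7.6.3), exposure (SAP 7.4.1) and deviations for study drug not given per protocol (SAP 7.2.2).

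**Working it through.** The plan gives no figure to reproduce. The check is whether the set of subjects allowed to resume overlaps the set to be discontinued.

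**Inputs**
- Concurrent clause (4.5.3): AST or ALT > 3 × ULN and total bilirubin > 2 × ULN.
- Grade ≥3 bullet (4.5.3): any drug-related AST, ALT or bilirubin at Grade 3 or above.
- Delay and resume rules (4.5.1, 4.5.2): Grade 2 AST, ALT and/or bilirubin.
- Grade limits: CTCAE version 4 (Section 5.3). The documents do not print them. Let Grade 3 begin above A × ULN for AST/ALT and above B × ULN for bilirubin.

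**Step 1: the overlap.** Values meeting the concurrent clause while both stay below Grade 3 satisfy

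3 < AST/ALT ≤ A and 2 < bilirubin ≤ B (in × ULN).

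This region is non-empty exactly when A > 3 and B > 2.

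| Assumed A | Assumed B | AST/ALT range | Bilirubin range |
|---|---|---|---|
| 5 | 3 | >3–5 | >2–3 |
| 4 | 2.5 | >3–4 | >2–2.5 |
| ≤3 | any | empty | empty |
| any | ≤2 | empty | empty |

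If Grade 2 starts no higher than 3 × ULN for AST/ALT and 2 × ULN for bilirubin (assumed starts: 3 and 1.5), every pair in the region is Grade 2 on both tests. The and/or wording would apply even if only one of the two were Grade 2.

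**Step 2: the instructions side by side, for a pair in that region**

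| Section | What it yields |
|---|---|
| 4.5.1 | Delay; not referred to 4.5.3, because neither value is Grade 3 |
| 4.5.2 | May resume at baseline values once any corticosteroid management is complete |
| 4.5.3, if the clause reaches Grade 2 | Permanent discontinuation, mandatory through 3.5 |
| 4.5.3, if the clause is confined to Grade 3 | Silent on this pair |

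**Step 3: does the clause reach below Grade 3?** The text points both ways.
- *It does:* the clause gives thresholds and no grade, and the bullet before it already covers every Grade ≥3 liver value. Confined to Grade 3, the clause would identify no new subject.
- *It does not:* the parent bullet is about Grade 3 laboratory abnormalities. A Grade 3-only clause would also keep one possible role, which is to remove the footnote's discretion when a Grade 3 AST or ALT comes with bilirubin above 2 × ULN.

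The redundancy argument therefore favours the wider reach but does not prove it.

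**Step 4: does 4.5.2 signal that it yields?** For another toxicity it does: "Adrenal insufficiency requires discontinuation regardless of control with hormone replacement". It has no matching sentence for the combined liver criterion. Section 4.5 lists the three sections without ranking them.

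**The case against.** The strongest reply is that the protocol already ranks its rules. Section 3.5 makes any 4.5.3 event a mandatory stop, while 4.5.2 grants only a permission. Section 4.5.2 also leaves most 4.5.3 rules unrepeated. Read alone, its opening sentence would let a subject with Grade 3 drug-related myocarditis restart after recovery, and nobody would read it so. The natural structure is that 4.5.2 serves subjects not already stopped under 4.5.3.

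Much of this stands. A reader might infer that the protocol gives two equal and opposite orders, and that a stopping site and a re-treating site would both comply. The documents do not support that. If the concurrent clause is met, Section 3.5 governs and the permission falls away. The re-treating site is covered only if it reads the clause as confined to Grade 3. What 3.5 leaves open is whether the clause is met by a Grade 2 pair, and 4.5.1, which refers only Grade ≥3 liver values onward, encourages the narrow reading.

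Three other tempting extensions also fail.
- *All combined sub-Grade 3 elevations are affected.* Only pairs above both thresholds are. Bilirubin between 1.5 and 2 × ULN with Grade 2 ALT raises no conflict.
- *Gilbert syndrome makes the conflict more likely.* Section 3.3.1 caps bilirubin at 1.5 × ULN "except subjects with Gilbert Syndrome who must have a total bilirubin level of" below 3.0 × ULN, so such a subject may enter above the clause's bilirubin threshold. That is a question about applying the clause to a raised baseline. The 4.5.1 rule and the parent bullet in 4.5.3 concern drug-related abnormalities, and the documents give no frequency.
- *The hepatic tables depend on which section is followed.* They count laboratory values. Only the length of the on-treatment window could change. Cases meeting the full Section 6.6 definition are reported as SAEs either way.

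Two cautions remain. Bullet nesting was read from extracted text and should be checked against the original layout. The hepatic algorithm in Appendix 3 was not available for review, so nothing is inferred from it.

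**Conclusion.** Wrong as written: an internal inconsistency in wording. For drug-related AST/ALT above 3 × ULN with bilirubin above 2 × ULN, both below Grade 3, Sections 4.5.1 and 4.5.2 read as delay and possible resumption, and 4.5.3 lists the pair for permanent discontinuation. The placement of the 4.5.3 clause lets a site exclude the Grade 2 pair from it.

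The conflict zone exists for any Grade 3 limits above 3 and 2 × ULN. Its extent, AST/ALT >3–5 with bilirubin >2–3 × ULN, rests on assumed limits of 5 and 3 × ULN. The link to liver injury holds for the laboratory thresholds only, because Section 6.6 adds conditions that 4.5.3 does not.

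The point matters for safety and deserves correction. It ranks below a must-fix defect because Section 3.5 resolves it in part. No view is taken on which instruction is clinically right.

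**What to change.** - Reconcile Sections 4.5.1, 4.5.2 and 4.5.3, together with 3.5, so that this combination has one instruction. The sponsor's medical team decides which one stands.
- State in 4.5.3 which grades the concurrent clause covers, and place it so that its parent bullet does not suggest otherwise.
- Cross-reference the clause in the Grade 2 liver bullet of 4.5.1 and in the and/or bullet of 4.5.2.
- As a separate item, say how the clause applies to subjects with Gilbert syndrome admitted with bilirubin above 2 × ULN.

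The cost is wording in the next amendment, or in an administrative letter if the sponsor judges the change to be clarification only. It needs no new tests, visits or data collection, and no change to the statistical analyses.
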